### 3.2 Rationale for study design

We will use a randomized controlled trial design to minimize selection bias and we aim to study advantages and disadvantages of MIS in relation to open approach in scoliosis surgical correction. The study uses a pragmatic approach and uses already available surgical techniques and infrastructures, such as already applicable minimal invasive approaches and existing navigation systems, hospital and quality registries, and picture archiving and communications systems.

Clinical Study Protocol	Unique protocol ID	MISCOS
	Version No:	1.1
	Date:	2025-09-27

Randomization to MIS or open surgery will be done within the Swespine registry-platform or in RedCap. Randomization will be stratified by country. Randomization lists will be prepared in advance by an independent statistician or data manager and will be concealed for the researchers.

Study visits are shown in Table 1. Patients will be assessed before surgery, during surgery and inpatient stay, at 3 months, 2 years and through the Swespine registry at 1, 2, 5 and 10 years. There will also be a 2-4 week surgical wound control by the health care personnel. There will be no additional visits for the patient involved in the study compared to the clinical routine.

**Table 1.** Study activities.

Day:	Visit 1 Screening Initial visit	Visit 2 Inpatient stay/surge- ry	Visit 3 outpatient clinic by Health care personnel 2-4 weeks	Visit 4 3 months	Visit 5 2 years
Informed consent	X				
Demography	X				
Inclusion/exclusion criteria	X				
Randomization		X***			
Surgical wound control			X		
Standing x-rays	X			X	X
2-year low-dose CT and standing x-ray control					X
Outcome assessments	X	X	X*	X**	X**

\*Outcomes related to wound control (SSI)

\*\*Outcomes assessed at regular clinical follow-ups; complications, SSI, readmissions and reoperations. SRS-22r, EOSQ-24, ODI, EQ-5D-5L questionnaires collected as per Swespine routine on web or paper (preop, 1, 2, 5 and 10 year postop).

\*\*\* Randomization will be done approximately a week prior to operation

## 4 STUDY POPULATION

### 4.1 Inclusion criteria

- Written informed consent
- Idiopathic scoliosis
- Age between 10-25 years
- Posterior correction for scoliosis
- Major curve Cobb angle 75 degrees or less

Clinical Study Protocol	Unique protocol ID	MISCOS
	Version No:	1.1
	Date:	2025-09-27

## 4.2 Exclusion criteria

- Inability to give informed consent
- Other diagnosis of scoliosis than “idiopathic”
- Rigid curves that require posterior or three-column osteotomy/ies
- Previous surgery at the operated levels
- BMI > 35
- Psychological factors that make the patient unsuitable for inclusion in the study (e.g., substance abuse, developmental disability)

## 4.3 Subject enrollment and randomization

Individuals scheduled for spinal deformity surgery will be informed of the study at the time of an outpatient visit.

Subject eligibility will be established before treatment randomization. Subjects will be randomized sequentially approximately a week before operation, as subjects are eligible for randomization. If a subject discontinues from the study, the subject number will not be reused, and the subject will not be allowed to re-enter the study.

## 4.4 Discontinuation and withdrawal of subjects

Subjects are free to discontinue their participation in the study at any time. This will not affect further treatment. Patients will be withdrawn from study if the patient withdraws consent. Already collected study data for these patients will be kept in the study database, however new data, including data from registries will not be added.

### 4.4.1 Premature termination of the study

The study group may decide to stop the trial or part of the trial at any time. Furthermore, the investigator should promptly inform the Ethics Committee and provide a detailed written explanation.

## 4.5 Re-screening

Re-screening for study inclusion is allowed before surgical treatment has been performed.

## 5 STUDY TREATMENTS

All treatments involve surgical stabilization and fusion of the deformed spine.

All forms of treatment are available and used today. The choice and use of 3D-imaging, navigation and RAS, or freehand are based on the preference of each surgeon. Navigated placement of pedicle screws is done according to local routines. Intraoperative cone beam computed tomography (CBCT) or preoperative low-dose CT can be used. The choice of supplier and brand of spine implants are based on the preference and availability in each center.

### 5.1 Minimal invasive scoliosis surgical correction- intervention group

Patients operated with MIS: Minimal invasive surgery. The surgeon will be free to choose the method of screw placement. 3D-navigation, RAS, free hand technique or combinations

Clinical Study Protocol	Unique protocol ID	MISCOS
	Version No:	1.1
	Date:	2025-09-27

of these may be used for screw placement. A long skin incision and subcutaneous multiple short incisions are performed. The erector spinae musculature is not detached from the spinous processes and the laminae, except for the exposure needed for the actual screw insertion. Each screw is inserted through an incision in the musculature. After placement of the screws, the positioning is checked with an intraoperative computed tomography. Misplaced screws may be repositioned or extracted. After implant placement, rods are bent to the desired shape and placed. Correction of the deformity and fixation is performed.

The surgeon may choose to do decortication of all or some of the facet joints in the surgical area. Decortication is performed by a navigated high-speed burr or other technique in a minimally invasive way. Finally, the wound/s is/are closed.

## 5.2 Open scoliosis surgical correction- control group

Patients operated with open surgery: Traditional open surgery. The surgeon will be free to choose the method of screw placement. 3D-navigation, RAS, free hand technique or combinations of these may be used for screw placement. A long skin and subcutaneous incision is performed. The posterior elements of the spine are exposed and the spinal musculature is detached from the posterior elements of the spine. The whole surgical area is exposed and all screws are inserted through this area. Separate incisions for screw placement in the musculature are not needed. After placement of the screws, the positioning is checked with an intraoperative computed tomography. Misplaced screws may be repositioned or extracted. After implant placement, rods are bent to the desired shape and placed. Correction of the deformity and fixation is performed. The surgeon may choose to do decortication of all or some of the facet joints in the surgical area. The surgeon may choose to do decortication of the spinous processes and laminae in the surgical area. Decortication is performed by a high-speed burr or other technique. Finally, the wound is closed.

## 5.3 Pre- and perioperative 3D-imaging, navigation and RAS

Navigation is done based either in intraoperative computed tomography, surface matching, augmented reality surgical navigation or infrared surgical navigation. Surface matching and infrared surgical navigation are based on the recognition and require detection of optical markers on a reference frame attached to a bony prominence of the spine. Augmented reality surgical navigation will show the entry point and direction of the planned screws on an augmented reality image screen in the operating theater.

In the end, navigation will result in a three-dimensional image of the spine in which screws are placed according to one of the following methods:

- The surgeon places the screws manually following the image and the virtual screw placement on the screen
- The surgeon places the screws through a robotic arm [Robotic Assisted Surgery (RAS)]. Prior to screw placement the surgeon plans the position of the screws on the preoperative low dose CT or the perioperative CBCT.

Clinical Study Protocol	Unique protocol ID	MISCOS
	Version No:	1.1
	Date:	2025-09-27

- If the surgeon prefers to use the free hand technique in combination with an intraoperative computed tomography verification of screw positioning, or other means to identify screw placement this is also possible.

## 5.4 Blinding

The study design does not allow blinding of the surgeons and other personnel in the operating theatre. However, the patient and other health-care personnel will be blinded and held up to two years postoperatively. Patient reported outcomes will be assessed without influence of the caregiver.

## 5.5 Randomization

The subjects are randomized in a 1:1 ratio, for MIS or open technique treatment arms. Randomization will be performed through the web-based platform of the Swespine registry (or similar platforms like RedCap) using an allocation sequence hidden from the healthcare personnel and provided independent from the study. Block randomization will be used. Block sizes will be unknown for the researchers. The inclusion will end when the sample size has been reached in both intervention arms.

### 5.5.1 Technical problems encountered during surgery

If a technical problem with the 3D/navigation system or RAS system is encountered during surgery, the patient will be kept in the group to which he or she was randomized. This means that a possible MIS approach needs to be converted to open technique to enable screw placement by free hand technique. The patient will remain in the group to which he or she was randomized to and will not be replaced.

## 5.6 Concomitant medication

Patients will receive their ordinary medications and the standard pre- and postoperative treatment.

## 5.7 Surgical data and complications

Detailed surgical data will be collected through hospital files, radiographs, Swespine or similar platforms. Additional spine surgeries (diagnosis and type of surgical procedure) will be identified in Swespine (or similar platforms) and the hospital files. Adverse events (postoperative infection, deep vein thrombosis and pulmonary emboli) will be collected from the hospital files and Swespine.

## 5.8 Imaging

Normal imaging and time points are as follows: Standard preoperative investigations include a whole spine standing radiograph, a whole spine bending radiograph and magnetic resonance imaging (MRI) of the spine. A preoperative low-dose CT or an intraoperative CBCT is always performed prior to screw placement. Screw placement is verified by a CBCT intraoperatively. The minimum radiologic follow-up includes a whole spine standing radiograph at the 3-month follow-up and a low-dose CT along with a standing radiograph at the 2-year follow-up. Curve size, type of scoliosis and other radiological parameters will be registered.

Clinical Study Protocol	Unique protocol ID	MISCOS
	Version No:	1.1
	Date:	2025-09-27

## 6 STUDY MEASUREMENTS AND VARIABLES

### 6.1 Primary variables

1. Reoperation within 2 years: A reoperation is defined as a secondary surgical procedure related to the index procedure and involving the spine at any level after the index procedure.
2. Serious complication: A life-threatening complication or a complication related to substantial invalidity (like pneumothorax or spinal cord injury).
3. Early SSI. It is defined as SSI with onset up to 12 weeks postoperatively.
4. Other systemic infection related to inpatient stay: Like pneumonia or UTI
5. Pain at 2 years f-u will be assessed with the numeric rating scale (NRS) for back pain measured on a scale from 0 (no pain) to 10 (worst possible pain). Data will be collected from Swespine or similar platforms.
6. SRS-22r: The SRS-22r is a scoliosis specific questionnaire aiming to estimate quality of life in patients with scoliosis [1]. It contains 24 items divided into 5 domains covering function, pain, self-image, mental health, and satisfaction. An index value is calculated for each domain and a total index value is possible to calculate ranging from 1 (worst) to 5 (best). SRS-22r will be collected from Swespine or similar platforms.
7. Radiologically healed fusion: A radiologically healed fusion is defined as bone bridging along the operated levels according to the preoperative plan. A vertebral segment will be considered fused if one of the following conditions is satisfied:
  - a. Bone bridge over at least one facet joint
  - b. Bone bridge between the vertebral bodies

### 6.2 Secondary variables

The secondary variables are listed below.

1. Inpatient stay in days.
2. The deformity correction rate will be assessed as Cobb-angle correction in a postoperative x-ray from the first standing radiograph compared to the last preoperative radiograph. The correction of the curve will be calculated according to the formula:  $(\text{preoperative Cobb angle} - \text{postoperative Cobb angle}) / (\text{preoperative Cobb angle}) \times 100\%$ .
3. Progression of Cobb angle in the operated levels at 2-years standing x-ray compared to the 3-month (first follow-up) x-ray. The progression of the curve will be calculated according to the formula:  $(\text{2-year Cobb angle} - \text{3-month Cobb angle}) / (\text{2-year Cobb angle}) \times 100\%$ .
4. Progression of secondary curve angles at 2-years standing x-ray compared to the 3-month (first follow-up) x-ray. The progression of the curve will be calculated according to the formula:  $(\text{2-year Cobb angle} - \text{3-month Cobb angle}) / (\text{2-year Cobb angle}) \times 100\%$ .
5. Perioperative blood loss (in mL).

Clinical Study Protocol	Unique protocol ID	MISCOS
	Version No:	1.1
	Date:	2025-09-27

6. Total procedure time (from incision to closure) as well as normalized to number of spinal levels from the upper to the lower instrumented vertebra (in min).
7. Accuracy at first attempt: Screws that are not placed and screws that are placed but repositioned after intraoperative verification are noted in the protocol. Accuracy of screw placement will be assessed as a score, calculated as the number of correctly placed screws divided by the total number of screws specified in the protocol (see Appendix 1 in the study protocol). The maximum score is 1, indicating perfect placement according to the preoperative plan. Screws graded Ia or Ib by the Heintel classification [2] are defined as correctly placed. Screws that are not inserted, or that require repositioning after intraoperative verification, will be recorded in the protocol and classified as NOT correctly placed.
8. Intraoperative neurophysiological monitoring. Neurophysiological monitoring is always performed as routine during spinal deformity surgery, with the exception of patients that are non-ambulatory. Motor evoked potential, sensory evoked potential and electromyography data will be collected to investigate any changes in neurophysiological parameters. Any deviations will be noted.
9. Health economics: Total cost per patient during the first 2 years of the study including cost of possible re-admissions and reoperations related to index surgery. Data on costs on the individual level will be collected. These consist of costs for the inpatient and outpatient visits (including surgery, radiographs, navigation), analgesic and antibiotic treatments as well as possible re-admissions related to index surgery.
10. Patient reported outcome measures. Collected from Swespine or similar platforms after 1, 2, 5 and 10 years.
  - a. SRS-22r: The SRS-22r is a scoliosis specific questionnaire aiming to estimate quality of life in patients with scoliosis [1]. It contains 24 items divided into 5 domains covering function, pain, self-image, mental health, and satisfaction. An index value is calculated for each domain and a total index value is possible to calculate ranging from 1 (worst) to 5 (best).
  - b. EOSQ-24 is a proxy answered questionnaire and will be used in individuals up to the age of 15. It consists of 24 questions of daily function, pain, pulmonary function and mobility [3].
  - c. Oswestry Disability index (ODI) is used in individuals from 15 years and older. ODI is a back specific index measuring disability due to back pain [4]. It is the recommended instrument for studies concerning back pain. An index from 0-100 is calculated. An ODI of 0–20 indicate minimal disability, 21–40; moderate disability, 41–60; severe disability, 61–80; severely crippled, 81–100; bed-bound.
  - d. EQ-5D 3 level is a generic quality of life instrument and consists of five areas reflecting mobility, self-care, usual activities, pain/discomfort and anxiety/depression [5]. Response alternatives range from no problems to extreme problems. An index can be calculated and depending on baseline value set used the index runs between approximately -0.5 (worst possible health) to 1.0 (best possible health). The EQ-5D-3L will be used for health economic analyses. The EQ-VAS is part of the EQ-5D and registers the patient's self-rated health on a visual analogue scale (from 0 to 100; best).

Clinical Study Protocol	Unique protocol ID	MISCOS
	Version No:	1.1
	Date:	2025-09-27

- e. Postoperative pain relief assessed by NRS at discharge. Additionally, given and prescribed doses of analgesics that follow clinical routine protocols will be registered from the hospital files.

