### **Secondary objectives related to operative technique**

Clinical Study Protocol	Unique protocol ID	MISCOS
	Version No:	1.1
	Date:	2025-09-27

- Deformity correction rate assessed as Cobb-angle correction in a postoperative x-ray from the first standing radiograph compared to the last preoperative radiograph. The correction of the curve will be calculated according to the formula: (preoperative Cobb angle - postoperative Cobb angle) / (preoperative Cobb angle) × 100%.
- Progression of Cobb angle in the operated levels at 2-years standing AP/PA x-ray compared to the 3-month standing AP/PA x-ray.
- Progression of secondary curves at 2 years f-u compared to the 3-month x-ray.
- Perioperative blood loss.
- Technical accuracy of screw placement at first attempt.
- Total procedure time (from incision to closure) as well as normalized to number of spinal levels from the upper to the lower instrumented vertebra.
- Accuracy of screw placement at first attempt (see 6.2)
- Intraoperative neurophysiological monitoring (see 6.2). Any incidences are recorded.

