#### 7.2.2 Secondary variables

For the secondary variables descriptive statistics will be used to characterize the data; means and 95% confidence intervals will be used for parametric data, medians and interquartile ranges for non-parametric data, and number (proportions) for categorical data. For groups comparisons t-test or ANOVA will be used for parametric distributed data and Wilcoxon, Mann-Whitney or Kruskal-Wallis test will be used for non-parametric distributions respectively, along with post hoc analysis. Categorical data will be compared with Chi-square, McNemar or Sign tests.

Clinical Study Protocol	Unique protocol ID	MISCOS
	Version No:	1.1
	Date:	2025-09-27

Data from the different groups will be compared based on the 'intention to treat' principle. An intention to treat (ITT) analysis means that all patients, regardless of treatment change, loss to follow-up or drop-out, remain in the analysis of the group to which they were randomized. Statistical expertise blinded for treatment allocation will perform the statistical analyses.

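### The Cobb progression formulas divide by the 2-year angle although progression is measured from the 3-month film, so a doubled curve is reported as 50% and a halved curve as -100%

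*Protocol*

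**What the plan says.** Two secondary variables measure whether the correction holds after surgery. In Protocol section 6.2, item 3 is "Progression of Cobb angle in the operated levels at 2-years standing x-ray compared to the 3-month (first follow-up) x-ray" and item 4 is "Progression of secondary curve angles at 2-years standing x-ray compared to the 3-month (first follow-up) x-ray". Section 2.2 names the same reference film for both: "Progression of Cobb angle in the operated levels at 2-years standing AP/PA x-ray compared to the 3-month standing AP/PA x-ray" and "Progression of secondary curves at 2 years f-u compared to the 3-month x-ray".

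Items 3 and 4 carry the same formula. With its typesetting code, it contains "2-year Cobb angle} - \text{3-month Cobb angle}) / (\text{2-year Cobb angle". The numerator is the 2-year angle minus the 3-month angle, and the denominator is the 2-year angle.

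Item 2, the correction rate, is built the other way. It is described as a comparison with the last preoperative film, and its formula is "preoperative Cobb angle - postoperative Cobb angle) / (preoperative Cobb angle) × 100", so the earlier film is the denominator.

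Section 7.2.2 says how such values are summarised: "means and 95% confidence intervals will be used for parametric data, medians and interquartile ranges for non-parametric data".

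**The concern.** A percentage change described as a comparison with the 3-month film would ordinarily have the 3-month angle as its denominator. The printed formulas use the later angle, and the protocol gives no reason for departing from the convention of item 2.

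The introduction says that MIS should not come at the cost of correction, and these two variables show whether correction is maintained. As printed, a reader of the trial report would see figures for progression since 3 months that are too small when the curve worsens and too large in size when it shrinks. Group means, which section 7.2.2 allows, would be pulled towards less progression in both arms.

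**Working it through.** **Inputs.** The formula and the reference film come from sections 2.2 and 6.2. The protocol states no numerical result for these variables, so there is no figure to reproduce.

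**Identity.** Let a be the 3-month angle and b the 2-year angle, both positive.

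- Change relative to the stated reference: Q = (b - a)/a.
- Printed formula: P = (b - a)/b.
- Since b = a(1 + Q), P = Q/(1 + Q).
- The gap is Q - P = Q²/(1 + Q), which is never negative.

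P is therefore at or below Q for every patient. It cannot reach 100% however far the curve worsens, and it has no lower bound as the 2-year angle approaches zero.

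**Exact values, starting from 20 degrees at 3 months.** The percentages depend only on the ratio of the two angles.

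| 2-year angle (degrees) | Printed formula | Relative to 3 months |
|---|---|---|
| 22 | 2/22 = 9.1% | 2/20 = 10% |
| 25 | 5/25 = 20% | 5/20 = 25% |
| 30 | 10/30 = 33.3% | 10/20 = 50% |
| 40 | 20/40 = 50% | 20/20 = 100% |
| 15 | -5/15 = -33.3% | -5/20 = -25% |
| 10 | -10/10 = -100% | -10/20 = -50% |

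A 20% increase (20 to 24 degrees) is reported as 4/24 = 16.7%.

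**Plausible progressions.** The protocol gives no residual angles or measurement error, so the following inputs are assumptions: mean residual curve 15 to 25 degrees, between-patient SD 5 degrees, reading error 2 to 3 degrees per film, and readings floored at 1 degree.

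| True progression | Mean residual | Median, printed formula | Median relative to 3 months |
|---|---|---|---|
| 5 degrees | 15 | 25% | 33% |
| 5 degrees | 25 | 17% | 20% |
| 3 degrees | 15 | 17% | 20% |
| 3 degrees | 25 | 11% | 12% |

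**No true change, same assumptions (1,000,000 curves per setting).**

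| Mean residual, reading error | Mean, printed formula | Mean relative to 3 months |
|---|---|---|
| 15, 3 | -9.2% | +9.1% |
| 15, 2 | -3.6% | +3.7% |
| 20, 3 | -3.5% | +3.5% |
| 20, 2 | -1.4% | +1.4% |
| 25, 3 | -1.8% | +1.8% |
| 25, 2 | -0.8% | +0.8% |

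Both medians are 0 and the mean change in degrees is 0.0 throughout. The mean of either percentage is thus distorted by reading error when the residual angle is small, in opposite directions. A two-patient example shows why. One curve goes from 15 to 30 degrees and another from 30 to 15, so the mean change is 0 degrees. The printed formula averages (50 - 100)/2 = -25%, and the 3-month percentage averages (100 - 50)/2 = +25%.

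**Effect on tests.** P is an increasing function of Q, so patients keep the same order and rank tests give the same p-value. In 4,000 simulated trials per setting, with 72 patients per arm and a 2-degree difference between arms, power across the six settings was:

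| Scale | t-test | Mann-Whitney |
|---|---|---|
| Printed percentage | 62-98% | 73-98% |
| 3-month percentage | 44-97% | 73-98% (same in every setting) |
| Degrees | 80-99% | 78-99% |

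Changing the denominator alone therefore gains no power. Any gain comes from analysing degrees.

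**The case against.** The strongest reply is that comparing one film with another only names the two films. It does not say that the result is a percentage of the 3-month angle. The formula is explicit, computable and the same in both items, and no stated figure is wrong. That is fair as far as it goes, but the printed denominator still departs from the natural reading and from the protocol's own practice in item 2, without a reason.

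Several further points stand and limit the weight of the finding:

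- The same formula applies in both arms, the sign of the change is preserved and rank tests are unaffected.
- At modest progressions the gap is small, for example 11% against 12%. Doubling and halving lie outside the 3- and 5-degree progressions assumed above.
- Both angles are recorded, so either version can be computed later.
- The null-mean and power results do not favour the 3-month percentage over the printed one. They argue for degrees, which is a separate point from the denominator error.
- The largest null mean depends on the assumed floor. In that setting the printed formula's mean is about -11.8% with a floor of 0.5 degrees, -7.4% with 2 degrees and -5.2% with 5 degrees.
- Correcting the denominator would match item 2 only in the convention of dividing by the earlier film. The two percentages would still have different bases (preoperative and 3-month angle) and could not be set directly side by side.

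**Conclusion.** The concern holds. Both formulas use a denominator that does not fit the stated reference film, and each reported non-zero change falls below the change from that reference. That conclusion is algebra and rests on no assumption beyond positive angles. Its practical size does depend on assumed residual angles: under those above, the median understatement runs from about 1 percentage point (12% reported as 11%) to about 8 (33% reported as 25%).

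The error lies in the reported values and means of two unranked secondary variables. It does not touch the primary endpoint, the sample size or any rank-based comparison. It should be corrected, but it does not threaten the trial's main conclusion.

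**What to change.** In section 6.2, items 3 and 4, define progression as the 2-year minus the 3-month Cobb angle in degrees, and compare the arms on that. If a percentage is also wanted, use (2-year - 3-month)/(3-month) × 100%. Summarise it by median and interquartile range, because reading error pulls its mean upward when the residual angle is small. Replacing the denominator alone would remove the inconsistency. Degrees are recommended in addition, because either percentage is unstable when its denominator is small.

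The cost is two formula lines. Standing films at 3 months and 2 years are already scheduled (Table 1 and section 5.8), so no new data are needed. Section 11 lists a change of secondary variable among substantial amendments, so the Ethical Review Agency may have to be informed. With enrolment starting in mid 2025, the first 2-year films fall around mid 2027. A correction made before then cannot be read as driven by results.
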